# STATISTICAL ANALYSIS PLAN

- NOSE Score
- Breathe VAS Score
- Sleep Apnea
- Nasal Surgery
- Epworth Sleepiness Scale

Five data sets will be imputed from these covariates and will mimic different realizations of the missing data. Within each imputed (complete) dataset for the primary endpoint, the proportion experiencing the endpoint will be statistically compared between treatment group using the two-sample z-test. For the primary endpoint, the numerator of the test statistic (the numerator is the point estimate of the treatment difference for the primary endpoint) and its standard error (the pooled standard error of treatment difference for the primary endpoint) will be pooled across the 5 data sets using established variance-adjustment methods (e.g., via PROC MIANALYZE in SAS) to create one overall numerator and denominator. From these, an overall test statistic for the endpoint and its associated p-value will be calculated for the imputed data.

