#### 2.4 Sample Size Considerations

The primary analysis will be based on a 1-sided binomial test of proportions. Assuming a Sham Control response rate of 40% and a Latera Treatment response rate of 70% at month 3, a maximum sample size of 124 evaluable subjects is required for 90% power and preserving a 2.5% (one-sided) type I error rate. This study is designed as a group-sequential trial with 2 interim analyses and a final analysis. The stopping boundaries are derived using the Triangular

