# STATISTICAL ANALYSIS PLAN

Method, which is a special case of Unified Family (Power) boundaries. A shape parameter of 0.65 will be used, and both boundaries will be non-binding.

Interim analyses will occur when approximately 20 and 60 total subjects have been enrolled and have had their 3-month assessment. The Latera response rate has been observed at approximately 85% in single-arm trials and is likely to be slightly lower in a single blind setting. Thus, 70% is likely a conservative estimate. The placebo response rate observed in pain trials is approximately 30%, and may be even higher in a procedural setting, so 40% was selected for the control response rate used in the study design calculations.

Assuming up to a 10% drop out rate and a 10% potential retrieval rate, the sample size is adjusted to enroll up to 150 subjects to assure adequate sample size with 3 months follow up.

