#### 2.7 Retrievals and Re-Implantation

There is a low incidence of where the Latera Implant is removed, post-implant nasal manipulation by a patient. If this occurs, the Latera Implant may be re-implanted, within 30 days, of the removal at the discretion of the investigator, continuing the follow up schedule from the Index Procedure. An addendum to the Informed Consent is required to be reviewed and signed by subject. See Section 4.1.1 for analysis implications.

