#### 5.5 Missing or Incomplete Data

Every effort will be made to minimize the amount of missing data. Recognizing the difficulty of avoiding some missing data, however, data imputation methods with sensitivity imputation analyses will be conducted as secondary analyses for the primary endpoint in the ITT and mITT populations. The robustness of the multiple imputation-based sensitivity analyses for the primary outcome will be tested with a tipping point analysis encompassing all possible imputation outcomes.

As a secondary sensitivity analysis in the ITT and mITT populations, multiple imputation of the primary endpoint will be carried out using the logistic regression approach for a dichotomous outcome with PROC MI in SAS for patients missing data for the 3-month assessment. The following baseline variables will be included in the imputation model as covariates:

- Age
- Gender
- Body Mass Index (BMI)
- Nose Length
- Nose Height
- Nose Width
- Inferior Turbinate Hypertrophy
- Septal Deviation

<sup>4 Yan X, Lee S, Li N. Missing data handling methods in medical device clinical trials. J Biopharm Stat, 19, 1085-98, 2009.

ST 800-A

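### SAP 5.5 leaves randomised arm out of the multiple-imputation model, so the secondary ITT/mITT treatment difference shrinks by roughly the missing fraction

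*SAP*

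**What the plan says.** SAP 5.5 plans a sensitivity analysis of the primary endpoint in the ITT and mITT populations, in which "multiple imputation of the primary endpoint will be carried out using the logistic regression approach for a dichotomous outcome with PROC MI in SAS". The model is introduced with "The following baseline variables will be included in the imputation model as covariates". Thirteen variables follow: age, gender, BMI, nose length, height and width, inferior turbinate hypertrophy, septal deviation, NOSE score, breathing VAS, sleep apnea, nasal surgery and ESS. The section then says "Five data sets will be imputed from these covariates and will mimic different realizations of the missing data". In each completed data set "the proportion experiencing the endpoint will be statistically compared between treatment group using the two-sample z-test", and the five results are pooled with PROC MIANALYZE or a similar method.

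Randomised arm is not on the list, and no by-arm step is given. Protocol 6.5 leaves the imputation method to the SAP and adds nothing on this point. SAP 5.5 also plans a "tipping point analysis encompassing all possible imputation outcomes".

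**The concern.** The analysis step estimates an arm effect that the imputation step does not allow for. Randomisation balances the 13 baseline variables between arms in expectation, so they cannot stand in for arm. A missing Latera subject and a missing sham subject with the same baseline values get the same imputed response probability, which averages close to the pooled observed rate.

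The primary analysis uses the per-protocol population (SAP 3.1 and 4.1.1), which needs an in-window 3-month NOSE score and drops subjects unblinded early. SAP 5.5 is the only place that says how missing 3-month outcomes are handled in the randomised population, so it is the plan's check on the per-protocol result. If that check shrinks the effect by construction, a weaker ITT/mITT result could be read as fragility when it is an artefact of the imputation model.

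**Working it through.** **Inputs.** SAP 2.4: "Assuming a Sham Control response rate of 40% and a Latera Treatment response rate of 70% at month 3"; 124 evaluable subjects, up to 150 enrolled, one-sided 2.5%, 90% power. The Protocol synopsis gives 1:1 allocation. The missing fraction m is not given. SAP 2.4 has only "Assuming up to a 10% drop out rate and a 10% potential retrieval rate", so m is an assumption, shown from 5% to 17.3%. The top value is 1 − 124/150 = 26/150. It is an upper planning case, because a retrieved subject may be re-implanted, "continuing the follow up schedule from the Index Procedure" (SAP 2.7), and so may still have a 3-month score.

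**The plan's own figure.** A fixed design with unpooled variance needs 2 × (0.7×0.3 + 0.4×0.6) × (1.960 + 1.282)² / 0.30² ≈ 105 subjects in total (112 with pooled variance). Simulating the tabulated boundaries at 22, 60 and 124 evaluable subjects gives power 0.902 with futility followed and type I error 0.025 with futility ignored. The 124 reproduces, so the design rates are a sound basis for what follows. The SAP states no figure for the imputation itself.

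**Closed form, arm omitted, equal missingness.** The pooled observed rate is (0.70 + 0.40)/2 = 0.55.

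- Latera: (1−m)×0.70 + m×0.55
- Sham: (1−m)×0.40 + m×0.55
- Difference: (1−m)×0.30

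At m = 10%: 0.685 − 0.415 = 0.270. At m = 17.3%: 0.674 − 0.426 = 0.248. At m = 5%: 0.95 × 0.30 = 0.285.

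**Unequal missingness.** The difference is 0.30 × [1 − (mT×wC + mC×wT)], where w is each arm's share of the observed subjects. With 20% missing on Latera and 10% on sham, wT = 0.8/1.7 = 0.471 and wC = 0.529. Relative shrinkage is 0.2×0.529 + 0.1×0.471 = 0.153, and the difference is 0.254. Shrinkage is then a weighted average of the two missing fractions.

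**Simulation.** Settings: 75 per arm (all 150 randomised), data missing at random within arm at equal rates, 13 covariates unrelated to outcome, logistic imputation with a normal draw of the coefficients, 5 imputations, pooled-variance SE combined by Rubin's rules, and about 8,000 replicates per row (about 4,000 for the 17.3% null row). The 0.025 threshold is illustrative, since the SAP sets none for this analysis.

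| Quantity | Missing | Arm omitted | Arm included |
|---|---|---|---|
| Mean difference | 5% | 0.285 | 0.298 |
| Mean difference | 10% | 0.269 | 0.296 |
| Mean difference | 17.3% | 0.247 | 0.294 |
| Mean MI SE / empirical SD | 10% | 0.085 / 0.075 | 0.085 / 0.082 |
| Mean MI SE / empirical SD | 17.3% | 0.088 / 0.074 | 0.089 / 0.086 |
| P(one-sided p < 0.025) | 10% | 90.9% | 93.6% |
| P(one-sided p < 0.025) | 17.3% | 83.9% | 91.4% |
| Same, null (55% in both arms) | 10% | 1.5% | 2.4% |
| Same, null (55% in both arms) | 17.3% | 1.1% | 2.8% |

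**Checks.** With 68 per arm and 10% missing, the difference is 0.270 omitted and 0.298 included. Making one covariate prognostic (correlation 0.3) leaves the 10% and 17.3% means unchanged. A separate simulation of 2,000 trials per setting, with different covariate settings, gave 0.272 v 0.301 at 10% and 0.247 v 0.297 at 17.3%.

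**The case against.** *The text may be silent rather than wrong.* Arm is a design factor, the list is headed as baseline variables, and a programmer might well impute by arm. But the SAP says the data sets come from these covariates, which reads as the whole model. Adding arm later would be a change in the favourable direction, and SAP 5.4.3 requires changes to be documented as amendments.

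*The effect is small and conservative.* This stands. At the stated 10% drop-out ceiling the loss is about 0.03 in the difference and 2.7 points in the chance of p < 0.025. In the completed German study (Protocol 1.2), 29 of 30 subjects had 3-month responder data; at 1/30 missing the closed form gives 0.290. The reported SE barely differs between the two models. It is too large only relative to the true spread of the shrunken estimator.

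*Including arm can be worse for some subjects.* SAP 4.1.1 follows Latera-assigned subjects who do not receive the device for safety, so they may lack NOSE scores. Suppose 10% are missing per arm and the missing Latera subjects respond at 40%. The true difference is 0.9×0.70 + 0.1×0.40 − 0.40 = 0.270. Omitting arm gives 0.270 and including it gives 0.300. The agreement is a coincidence: pooled imputation overstates Latera (0.685 v 0.670) and sham (0.415 v 0.400) by the same 0.015. With the 10% missing on Latera only, wC = 1/1.9 = 0.526, and omitting arm gives 0.30 × (1 − 0.1×0.526) = 0.284, not 0.270. The example shows that results depend on why data are missing. It does not justify pooled imputation.

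*The tipping-point analysis covers it.* In part. It shows which imputed outcomes would change the conclusion, but it does not supply a valid missing-at-random estimate.

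**Conclusion.** The concern holds. As written, SAP 5.5 gives an ITT/mITT difference that is too small by about the missing fraction: roughly 0.27 instead of 0.30 at 10% missing, and 0.25 at 17.3%. This rests on the design rates and on data missing at random within arm; the shrinkage equals the missing fraction exactly only when missingness is equal in the arms. If missing Latera subjects are mostly failures, imputing about 55% would be optimistic instead.

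The per-protocol primary test and the group-sequential error rates are not affected. This is not a fatal fault, but it is a clear mismatch between imputation and analysis models in the plan's main robustness check, and it should be corrected before unblinding.

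**What to change.** Amend SAP 5.5 to include randomised arm in the PROC MI logistic model, or to run the imputation separately by arm. In simulation, arm as a covariate gives 0.296 at 10% missing and 0.294 at 17.3%; imputation by arm gives 0.294 and 0.289. The cost is one sentence of SAP text and one added variable or BY statement.

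As an option, add the 7- and 30-day NOSE scores, which the Protocol schedule already collects, with a stated rule for their own missing values. This adds information but does not replace the arm term: at an assumed correlation of 0.7, early NOSE without arm still gives only 0.282 at 10% and 0.272 at 17.3%.
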